10.4 General Considerations

Participants who have withdrawn consent for continuation of the study (i.e., dropouts or non-compliant) will be included in the analysis by modern imputation methods for missing data. In the unforeseen circumstance of a protocol violation (e.g., 20G PIVC instead of 22G PIVC; blood was collected into 6mL vacutainer before 2mL for a specific participant), the data will be analyzed ‘as treated’ – that is, data will be analyzed as the participant’s actual received intervention. However, in the unforeseen circumstance of a protocol violation whereby a participant receives the wrong intervention (e.g., two different gauge catheters; two 20G catheters of the same length), they will be treated as per protocol and thus their data will be excluded from the study.

10.5 Primary Endpoint(s)

Comparisons across and between device configurations (i.e., length/gauge) will be made using logrank tests for indwell time. The primary endpoint will be evaluated using statistical modeling software (Prism, Release 8.3; GraphPad Software Inc., USA) or R (R 3.6.2 or higher).

10.6 Secondary Endpoint(s)

Linear mixed-effects models will be used to evaluate the following endpoints over time and determine the effect on PIVC indwell time for a given configuration (i.e., length/gauge):

- 1) cfHb concentration;
- 2) blood draw fill time;
- 3) blood flow velocities above or below the catheter
- 4) vessel dimensions; and
- 5) intravenous thrombus size.

Underlying normality assumptions will be verified and if not fulfilled non-parametric tests will be used. Multivariate analysis (to be defined in the SAP) will be employed to assess the effect of baseline characteristics on catheter indwell time and thus identify their power as predictive biomarkers using the following the independent variables including, but not limited to:

- 1) angle of insertion;
- 2) vessel dimension;
- 3) presence of side branches and/or intravenous valves;
- 4) age;
- 5) sex;
- 6) height;
- 7) weight;
- 8) BMI;
- 9) medical history questionnaire responses; and
- 10) exploratory endpoints.

A multiple-logistic regression analysis will be employed to assess the effect of baseline characteristics on catheter failure over a period of 72 hours and thus identify their power as predictive biomarkers using the independent variables including, but not limited to:

- 1) angle of insertion;
- 2) vessel dimension;
- 3) presence of side branches and/or intravenous valves;
- 4) age;
- 5) sex;
- 6) height;
- 7) weight;
- 8) BMI;
- 9) medical history questionnaire responses; and
- 10) exploratory endpoints.

A chi squared analysis will be employed to assess the proportion of individuals in each group (i.e., PIVC length and gauge) that have presence of the following at failure/end-of-protocol:

- 1) vein collapse;
- 2) intravenous thrombus; and

3) extravenuous thrombus.

All data will be evaluated using statistical modeling software (Prism, Release 8.3; GraphPad Software Inc., USA) or R (R 3.6.2 or higher). P-values ≤ 0.05 will be considered statistically significant.

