2.4 Sample Size

There is limited published data investigating the impact of PIVC catheter length on indwell time; a single article was found in the literature comparing catheter survival between a BD PIVC catheter (20 gauge; 4.78 cm/1.88-inch length) and midline catheter (POWERWAND™, 19.5 gauge; 6 cm/2.3-inch length). The indwell time results for this research were utilized to calculate a sample size estimate using the routine “Survival - Two Survival Curves - Logrank Tests” available in the software PASS 2019. Based on the available dataset, a sample size of ~20 participants per PIVC length would be required, considering median failure times of catheter of different lengths of 1 and 3 days, as can be seen in Figure 2.4.1. The same calculation will be applied to investigating the impact of increased gauge, because the increased volume of catheters is similar in both condition (i.e., 1 versus 1.75 inch = 75% increased volume; 20 versus 22 gauge = 51% increased volume).

Figure 2.4.1: Details of sample size calculation

Logrank Tests

Numeric Results for the Logrank Test in Terms of Sample Size

Alternative Hypothesis: Two-Sided

Power	N1	N2	N	Haz Ratio (HR)	Ctrl	Trt	Acc-rual Pat'n	Acc-rual Time/Total Time	Ctrl Loss	Trt Loss	Ctrl to Trt		Alpha	Beta
					Med Surv Time (M1)	Med Surv Time (M2)					to Trt	to Ctrl		
0.8054	19	20	39	0.3333	1.00	3.00	Equal	0 / 3	0.0000	0.0000	0.0000	0.0000	0.0500	0.1946

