6. Summary statistics and boxplot showing time between time of initial thrombus observation and device removal per device configuration

7. Importance of covariates will be computed with Boruta algorithm with a survival random forest model (an example output from the algorithm is provided in the Appendix by Figure B.7.1).
8. Test of predictive performance for the most important features (confirmed by the Boruta algorithm) using a leave-one-out strategy

In addition to the variables used in the primary endpoint survival model (device gauge and length), investigated baseline characteristics will be:

- Venous thrombosis
- Thrombus Length
- Thrombus Type
- Angles of insertion (Acute Inferior and Superior)
- Catheter to vein (C/V) ratio
- Catheter length in vessel
- Presence of side branches and/or intravenous valves
- Age
- Gender
- Height
- Weight
- BMI
- Dominant arm
- Medical history questionnaire responses
- Exploratory endpoints:
 - Vein collapse
 - Phlebitis
 - Dislodgement
 - Extravasation
- item Screening Blood Testing (as provided by Blood Testing CRF)
 - Coagulation Panel: PT & aPTT
 - Platelet Aggregometry: ADP, TRAP & Collagen Induced Maximal Amplitude
 - Blood Screening: Blood Glucose & Triglycerides
 - Liver Panel: ALT Average Measurement & AST Average Measurement

The Boruta algorithm does not require specific formatting and generally works well with continuous and categorical variables. In some cases, it might be interesting to move from continuous format to a categorical one (e.g. age) depending on the final analysis. Categorization rules will be detailed whenever performed.

5.2.2.4 Evaluation of changes in vessel dimensions, PIVC position (insertion angle and *in situ* tip position), and haemodynamics from baseline throughout indwell time

These will be evaluated using:

- C/V ratio
- Catheter Length in Vessel (mm)
- Catheter Insertion Angle - acute inferior border angle (deg)
- Catheter Insertion Angle - acute superior border angle (deg)
- Blood Draw Time (sec)
- Blood Flow Velocity (cm/sec)
- *In situ* tip position (Mid-Stream & Wall Contact)

For each of these characteristics, summary statistics by indwell time considered as a discrete variable (0, 6, 24, 30, 48, 54, 72 hours) and line and bar plots will be generated on average for continuous and by proportion for categorical responses, respectively.

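### Protocol 10.6 keeps a 72-hour logistic model with ten or more predictors on about 25 expected non-failures, with no validation and no allowance for paired catheters; the SAP neither specifies nor withdraws it

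*Protocol*

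**What the plan says.** Protocol 10.6 commits to this analysis: "A multiple-logistic regression analysis will be employed to assess the effect of baseline characteristics on catheter failure over a period of 72 hours". Its aim is to "thus identify their power as predictive biomarkers", "using the independent variables including, but not limited to" ten listed items. Eight are single characteristics: insertion angle, vessel dimension, side branches or valves, age, sex, height, weight and BMI. The ninth, "medical history questionnaire responses; and" the tenth, exploratory endpoints, are blocks whose size is not given. Protocol 10.7 limits the tenth to exploratory endpoints collected at baseline. The only criterion in the section is "P-values ≤ 0.05 will be considered statistically significant".

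For this model the Protocol sets no limit on predictors, no penalisation and no internal validation, and it does not allow for each participant contributing two catheters. Protocol 10.1 leaves further statistical detail to the SAP, but the SAP does not mention the model. For the relation between characteristics and indwell time, SAP 5.2.2.3 uses a Boruta screen on a survival random forest, followed by this step: "Test of predictive performance for the most important features (confirmed by the Boruta algorithm) using a leave-one-out strategy". SAP 5.2.1.1 separately plans a Cox model with gender, age, BMI and dominant arm as covariates.

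**The concern.** A logistic model carries about as much information as its smaller outcome class allows. Here that class is catheters still working at 72 hours, and the model would spend it on many coefficients. Apparent discrimination is then inflated, and without a validation step nothing in the plan would show it. Testing every coefficient at 0.05 also makes a false lead likely in any one analysis, and treating the two catheters of a participant as independent adds to that. BMI is calculated from height and weight, so putting all three in one model makes their coefficients unstable. The yes/no outcome also scores a failure at 6 hours the same as one at 72 hours. What is at stake is the credibility of any characteristic reported as a predictive biomarker.

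**Working it through.** **Inputs.** 40 participants with one short and one long catheter each, so 80 catheters, 40 per length (Protocol 4.1). Follow-up is 72 hours, or 3 days. SAP 2.4 sizes the study "considering median failure times of catheter of different lengths of 1 and 3 days", with "Alternative Hypothesis: Two-Sided", alpha 0.05, N1 = 19, N2 = 20 and hazard ratio 0.3333.

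**The plan's own figure.** Exponential survival at 3 days is 0.5^(3/1) = 0.125 (short) and 0.5^(3/3) = 0.50 (long). Expected events are 19 × 0.875 + 20 × 0.50 = 26.6. Schoenfeld's formula gives power 0.809 and the Lakatos method 0.806, against the stated 0.8054. The exponential reading therefore matches the sponsor's calculation.

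**Outcome counts in the logistic model.** Failures: 40 × 0.875 + 40 × 0.50 = 35 + 20 = 55. Non-failures: 80 − 55 = 25 (simulated 95% range about 17 to 33). Other assumed medians give a smaller outcome class of 10 (1 and 1 day), 34 (2 and 3 days) or 40 (3 and 3 days). Even 40 gives only 40/10 = 4 per predictor.

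**Noise-only simulation.** Failure depends on catheter length alone, and every listed predictor is unrelated to failure. Two independently written simulations used different assumed block sizes: 8, 13 and 18 predictors in one (800 trials each), and 10, 14 and 19 in the other (2,000 each). The last two columns treat a participant's two arms as independent.

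| Predictors | Non-failures per predictor | Mean apparent AUC | At least one p ≤ 0.05 |
|---|---|---|---|
| 8 | 25/8 = 3.1 | 0.68 | 23% |
| 10 | 25/10 = 2.5 | 0.71 | 32% |
| 13 | 25/13 = 1.9 | 0.73 | 36% |
| 14 | 25/14 = 1.8 | 0.74 | 42% |
| 18 | 25/18 = 1.4 | 0.77 | 47% |
| 19 | 25/19 = 1.3 | 0.79 | 62% |

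The AUC in new data is 0.50, and participant-grouped cross-validation gives 0.48. With correlation 0.5 between a participant's arms, the last column becomes 37%, 51% and 68% for 10, 14 and 19 predictors. With a participant frailty (log-SD 0.7) it runs from 29% to 63% over 8 to 18 predictors.

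**Source of the false positives.** Repeat runs with ten times the participants gave 20–24%, 27–33% and 38–43% for 8, 13 and 18 predictors, against 22–23%, 33–38% and 46–50% at the planned size. The rate falls only modestly with more data, so it is mainly multiplicity. Within-participant correlation raises it further. The inflated apparent AUC is the part tied to the small sample.

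**Collinearity.** With 10 predictors the median variance inflation is about 58 (height), 158 (weight) and 102 (BMI). Standard errors are therefore multiplied by about √58 = 7.6, √158 = 12.6 and √102 = 10.1. The other simulation, with 8 predictors, gave 76, 197 and 126. BMI is not a linear function of height and weight, so the model can still be fitted.

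**The case against.** The strongest reply is that the SAP has in effect replaced this model. Protocol 10.6 also plans a multivariable analysis of indwell time on the same list, Protocol 10.1 hands detail to the SAP, and SAP 5.2.2.3 answers with a time-to-event method and a predictive check. The study is exploratory and has no acceptance criteria (SAP 2.9). The Cox model in SAP 5.2.1.1 already uses a single body-size measure. All of this lowers the practical weight of the point, but it does not close it. The logistic model is still in the Protocol. The leave-one-out check belongs to another method, and it covers only features that have already been selected.

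It is also fair that AUC is not named in the Protocol, and that the overall likelihood-ratio test stays near nominal (6–10% with independent arms, 8–19% with correlation 0.5).

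Four stronger readings are tempting and are not supported:

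- A reader might blame the false positives on having only 25 non-failures. The larger simulations show otherwise.
- A reader might infer that a catheter leaving early without failing must be dropped or counted as a success. Protocol 10.4 has an imputation rule for dropouts and 8.3 replaces lost participants. The conflict with SAP 5.2.5, which bars imputation, is a separate matter.
- A reader might infer that this model is meant to guide product decisions. Protocol 4.1 says that of the trial as a whole, and the outputs listed for early business use in SAP 2.6 do not include this model.
- A reader might say that body-size effects cannot be estimated, or that a real one would be hidden. The coefficients are unstable rather than inestimable, and no real effect was simulated.

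**Conclusion.** The point holds and should be fixed. As written, the model gives a mean apparent AUC of about 0.68 to 0.79 when the truth is 0.50. It flags at least one noise predictor in roughly 23% to 62% of trials, and somewhat more often when a participant's arms are correlated. Variance inflation for height, weight and BMI is about 60 to 200.

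The figure of 25 non-failures assumes exponential failure, the planning medians in both gauges, all 80 catheters analysed and no loss. Block sizes, covariate distributions and within-participant correlation are assumptions, because the documents do not give them. The AUC reference of 0.50 applies to the listed items. If gauge and length were added under the open-ended wording, part of the discrimination would be real. The primary comparison of indwell time is not affected.

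**What to change.** Delete the multiple logistic regression from Protocol 10.6 and reconcile that section, with 10.7, to SAP 5.2.2.3.

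For adjusted estimates, use the Cox model in SAP 5.2.1.1 with gauge and length, participant-clustered (robust) variance or a shared frailty, and a short predictor list fixed in advance with BMI as the only body-size measure. State whether insertion angle and pre-insertion vein diameter replace or add to gender, age, BMI and dominant arm. With gauge, length and four predictors there are 55/6 = 9.2 expected failures per coefficient; with six predictors, 55/8 = 6.9. Exempt this model from the SAP 5.2.4 rule of starting with all interactions and removing non-significant terms. Report concordance corrected for optimism by resampling participants.

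Keep the Boruta survival-forest screen, labelled exploratory. Leave out whole participants in its predictive check, and repeat the feature selection inside each fold.

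The cost is Protocol and SAP wording and somewhat less analysis. The downside is that fewer characteristics receive an adjusted estimate.

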Intervention(s)/Procedure(s)	After screening and enrollment, participants will be randomized in order of their enrollment to either 20 or 22G of the BD Nexiva™ PIVC and order of placement location (left or right arm first). The participant will have both the 1 inch and 1.75 inch PIVCs inserted on Study Day 1 (Visit 2), one into each arm. After successful insertion into the lower cephalic vein of the selected arm, the site will be regularly accessed (twice daily) for phlebotomy and then flushed. The site will be assessed visually for tissue effects, skin reactivity, and pain, and using ultrasound for vessel anatomy/dimensions, catheter tip location in the vessel, color, and PWD. After catheter removal there will be a final inspection of the insertion site and securement dressing, assessing for tissue effect, skin reactivity, and pain.		
Investigational Sites	This study is a single-center study that will be conducted at Griffith University Gold Coast Campus, Clinical Trials Unit in Queensland, Australia.		
Data Monitoring Committee	Not applicable.		
Regulatory Status	Registered with Australian TGA: ARTG 243114		

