4 STUDY DESIGN

4.1 Overall Design

This is a randomized, single-center, open-label feasibility trial to provide preliminary signals of performance to help make decisions about whether to continue with the development of product enhancements. Four variations of the BD Nexiva PIVC (20G x 1, 20G x 1.75, 22G x 1, or 22G x 1.75) will be placed in the lower cephalic vein of both arms in approximately 40 healthy volunteers; 20 participants with 20G x 1 inch and 20G x 1.75 inch catheters, and second group of 20 participants with 22G x 1 inch and 22G x 1.75 inch catheters. PIVC indwell time will be monitored (removal at 72 hrs or upon inability to flush/aspirate) with blood collected by venipuncture (Day 1 only) and via the devices using 2 and 6mL vacutainers throughout the remainder of indwell time.

After 5 participants have completed their final visit, the in-situ catheter positions will be compared to the expected tip position based on the catheter lengths (1 inch versus 1.75 inch for either gauge). Tip position of the longer catheter is expected to reside more horizontally within the vessel. In the event catheter tip position differences are not distinct between catheter device lengths study conduct may be stopped. Additionally, this analysis will be used to refine study logistics associated with device placement, securement, sonographic measurements, and blood sample acquisition/testing over the 72-hour study duration.

Each participant will complete 6 visits: a Screening Visit (V1), followed by 4 Visits (V2-V5) to be started within 30 days after screening, and a 24-96 hour follow-up post catheter removal (V6).

The duration of the study execution is expected to be 5 months.

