4.2 Scientific Rationale for Study Design

Given that participant variability (e.g., coagulation and platelet function) may impact study endpoints (e.g., device indwell time and haemolysis)²³, the current study utilizes a simultaneous paired experimental design to assess whether differences in device design (i.e., lengths of 1 inch and 1.75 inch) impact PIVC indwell time; unpaired analysis will be employed to investigate the effects of catheter gauge on PIVC indwell time. PIVC length was selected for paired analysis as it is hypothesized that longer PIVC catheters may extend indwell time based upon catheter tip location within the vessel, increased tip distance from insertion site, and reduced probability of accidental dislodgement. Although gauge is a factor that may impact indwell time, participant screening is conducted to only enroll those with catheter-to-vessel (C/V) ratios no greater than 45%; thus it is anticipated that gauge will have an effect less susceptible to participant variability and was selected for the unpaired analysis. As both device length and gauge are expected to influence haemolysis^{17,20} the study design enables evaluation of both design features.

Identification of device design factors that improve PIVC indwell time and decrease incidence of haemolysis during PIVC-based blood collection is of clinical significance due to the associated benefits for the patient (e.g., uninterrupted medical treatment, and decreased discomfort, pain and anxiety)^{28,29,33}, for the health care worker (e.g., reduced chance of needle stick injuries)²⁸, and for the healthcare institution (i.e., reduced cost of care)^{12,29}.

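### Protocol 10.6 compares thrombus and vein collapse between catheter lengths with an ordinary chi-squared test, although every participant carries both lengths

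*Protocol*

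**What the plan says.** **The test.** Protocol 10.6 lists vein collapse, intravenous thrombus and extravenous thrombus and states: "A chi squared analysis will be employed to assess the proportion of individuals in each group (i.e., PIVC length and gauge"). The groups are compared on those "that have presence of the following at failure/end-of-protocol". The same section sets the threshold: "P-values ≤ 0.05 will be considered statistically significant". It names no paired or cluster-adjusted version of the test.

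**The design.** Protocol 1.1 states: "The participant will have both the 1 inch and 1.75 inch PIVCs inserted on Study Day 1 (Visit 2), one into each arm". Gauge is allocated between people; Protocol 4.1 describes "20 participants with 20G x 1 inch and 20G x 1.75 inch catheters, and second group of 20 participants with 22G" catheters of the same two lengths.

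**The rationale.** Protocol 4.2 explains the choice: "Given that participant variability (e.g., coagulation and platelet function) may impact study endpoints (e.g., device indwell time and haemolysis"), "the current study utilizes a simultaneous paired experimental design to assess whether differences in device design". For gauge, "unpaired analysis will be employed to investigate the effects of catheter gauge on PIVC indwell time". Both statements concern indwell time.

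**The SAP.** Section 5.2.2.3 covers thrombus with summary statistics, plots, Boruta importance and a leave-one-out check of prediction. Section 5.2.3.1 covers vein collapse and venous thrombosis with frequencies, Boruta and association measures. The logistic mixed models with a subject random effect cover haemolysis (5.2.2.1) and tip position (5.2.2.4), but not thrombus or vein collapse. The chi-squared test does not appear in the SAP and is not withdrawn there.

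**The concern.** An ordinary chi-squared test takes the 1-inch and 1.75-inch groups as two independent samples. Here they are the two arms of the same 40 people. The test therefore uses the wrong variance for the length difference and gives up the within-person comparison that is the reason for placing both lengths in each participant.

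Thrombus presence is a named secondary endpoint, and length is the design factor that the sponsor is studying (Protocol 2.2). The rationale in Protocol 4.2 cites coagulation and platelet function as sources of participant variability. These bear on thrombus at least as directly as on indwell time, so a positive correlation between arms is the natural expectation. In that case the stated test could miss a length signal that a paired analysis of the same data would show.

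For gauge there is a separate question. If both catheters of each person enter the table as separate observations, positive correlation works in the opposite direction and makes the test too liberal.

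**Working it through.** **The plan's own figure.** The only power figure is 0.8054 in SAP 2.4, for the logrank test on indwell time. With medians of 1 and 3 days and 3 days of follow-up, the event probabilities are 1 − 2⁻³ = 0.875 and 1 − 2⁻¹ = 0.50. Expected events are 19 × 0.875 + 20 × 0.50 = 26.6. Schoenfeld's formula then gives 0.8088 and a Lakatos-type calculation 0.8057, so the figure reproduces. It has no bearing on the chi-squared comparisons, for which no power is stated.

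**Inputs.**
- From the documents: 40 people, one catheter of each length per person; 20 people per gauge; threshold 0.05.
- Assumed: within-person correlation ρ of 0.1, 0.3 and 0.5, with −0.2 as a check; event rates, because the documents give no planning rate for these outcomes.

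**Type I error.** Under the null hypothesis the chi-squared test uses the variance of a difference between independent groups.
- Length (paired): the true variance is (1 − ρ) times that, so the true size is 2Φ(−1.96/√(1 − ρ)).
- Gauge with catheters pooled, 40 v 40: the true variance is (1 + ρ) times that, so the true size is 2Φ(−1.96/√(1 + ρ)).

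For example, at ρ = 0.3 the length test gives 2Φ(−1.96/0.837) = 2Φ(−2.34) = 1.9%.

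| ρ (assumed) | Length | Gauge, catheters pooled 40 v 40 |
|---|---|---|
| 0.1 | 3.9% | 6.2% |
| 0.3 | 1.9% | 8.6% |
| 0.5 | 0.6% | 11.0% |

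Simulation with 60,000 trials per setting and an assumed 63% event rate agrees:
- Length: 4.1% / 2.0% / 0.6%.
- Gauge, pooled: 6.1% / 8.6% / 11.3%. With a continuity correction this falls to 3.7% / 5.6% / 7.6%.
- Gauge counted once per person (thrombus in either arm), or compared within one length: about 5% throughout.
- At ρ = −0.2 the directions reverse: length 7.3%, pooled gauge 2.7%.

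**Power for length.** Assume rates of 60% v 35% in 40 pairs. The probability that both arms are affected is 0.60 × 0.35 + ρ√(0.60 × 0.40 × 0.35 × 0.65) = 0.210 + 0.234ρ. At ρ = 0.3 this is 0.280. The discordant cells are then 0.60 − 0.280 = 0.320 and 0.35 − 0.280 = 0.070, or about 12.8 and 2.8 of 40 pairs. Simulated power:

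| ρ (assumed) | Chi-squared | McNemar | Exact McNemar |
|---|---|---|---|
| 0.1 | 64–65% | 66% | 57% |
| 0.3 | 66% | 76% | 68% |
| 0.5 | 68% | 90% | 85% |

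For length, McNemar's test has a size of 4.3% to 5.1% at event rates of 30% to 63% and ρ of 0.1 to 0.5.

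**The case against.** **The SAP may have replaced the test.** Protocol 10.1 defers detail to the SAP, which does not carry the chi-squared test and says in 5.2.4 that models are preferred to non-parametric tests. It is therefore uncertain that the test would be run. This stands in part: the defect is as much a mismatch between the documents as a wrong test. It does not remove the point, because the SAP names no test or model by length or gauge for presence or absence and does not say that the protocol's test is dropped. The gap is limited to presence or absence, since Protocol 10.6 assigns intravenous thrombus size to a linear mixed-effects model.

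**The gauge test may be sound.** A reader might infer that the chi-squared test is too liberal for gauge in every case. The documents do not support that. Protocol 10.6 speaks of individuals, gauge is randomized between people, and a comparison of 20 v 20 people keeps its size. Per-catheter counting is still a natural reading. The outcome is timed at each catheter's own failure, and mock Table A.10.2 counts 80 catheters at hour 0 from 40 people. The text does not settle the unit.

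**The size rests on an assumed correlation.** This stands. No figure is given, the gain at 0.1 is trivial, and the direction reverses if the correlation is negative. The exact McNemar test also gives back much of the gain: at 0.1 it has less power than chi-squared, and at 0.3 it is only about 2 points better.

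**The stakes are limited.** This stands too. Pairing is justified in Protocol 4.2 for indwell time, SAP 2.9 sets no acceptance criteria, and SAP 2.8.3 also lists vein collapse and venous thrombosis as exploratory.

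**Conclusion.** The point holds for length. The test stated in Protocol 10.6 treats paired arms as independent samples, whatever the counting convention, because each person belongs to both length groups. With positive within-person correlation it is conservative, and the power lost ranges from almost nothing at 0.1 to about 22 points (90% − 68%) at 0.5 under the assumed rates. These figures illustrate the direction and possible size; they do not predict what this trial will show.

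For gauge the conclusion is conditional. The test is too liberal only if a person's two catheters are counted separately, and less so with a continuity correction. What can be said without condition is that the unit of analysis is not stated.

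A reader might also infer that the study will miss a length effect on thrombus. The documents do not support that: they give neither the correlation nor the event rates, and they leave open whether the chi-squared test will be used. The change is worth making, but the consequence is modest.

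**What to change.** In Protocol 10.6, replace the chi-squared test. In SAP 5.2.2.3 and 5.2.3.1, add the same replacement for vein collapse, intravenous thrombus and extravenous thrombus at failure or end of protocol:

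- **Length:** McNemar's test on the participant pairs, with the exact version or conditional logistic regression when discordant pairs are few.
- **Gauge:** a person-level comparison, 20 v 20, for example on the number of affected arms.
- **Alternative to both:** one logistic mixed model or GEE clustered on participant, with gauge, length and their interaction, where events are frequent enough to fit it. The SAP already uses logistic mixed models with a subject random effect for haemolysis and tip position.
- **Unit:** state whether each analysis counts catheters or people.

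If the sponsor intends these outcomes to be descriptive only, both documents should say so and the chi-squared test should be withdrawn.

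The cost is wording and a little more analysis work; no extra participants or data are needed. There are two drawbacks. A mixed model on 40 clusters of two may be unstable for a rare outcome, as vein collapse may prove to be, and the exact McNemar test gives up some power.
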